### 5.3.6 Other Considerations

In case subjects who took combination therapy in Arm A and Arm B discontinue one treatment earlier than the other, end of treatment date is defined as the latest date of the last dose dates of two study drugs. All efficacy and safety endpoints will be summarized up to the end of treatment date plus applicable window for each endpoint.

## 5.4 Efficacy Analyses

### 5.4.1 Primary Efficacy Analyses

The primary endpoint PFS as assessed by IIR using RECIST 1.1 will be compared between lenvatinib + everolimus (Arm A) and sunitinib (Arm C), as well as between lenvatinib + pembrolizumab (Arm B) and sunitinib (Arm C). An interim and a final analysis of PFS are planned to be performed (SAP [Section 6](#)). Lan-DeMets spending function with O'Brien-Fleming boundary will be used to control alpha levels between the interim and final analysis of PFS (SAP [Section 5.3.3](#)). The interim analysis of PFS will be performed when it is approximately 4 months after the last subject is randomized and an approximately 80% information fraction of PFS events (as determined by the IIR) in Arm B and Arm C. The final analysis of PFS will be performed when approximately 388 PFS events, as determined by the IIR, are observed between each comparison. A graphical approach will be used to control the FWER at the two-sided 0.0499 for multiple comparisons, including both PFS, OS and ORR comparisons of Arm B vs Arm C and Arm A vs Arm C. For each comparison, a statistical significance can be claimed based on either interim or final analysis of PFS at specified alpha levels.

The PFS curve in each treatment group will be estimated using Kaplan-Meier (K-M) method and the difference in PFS for the 2 primary comparisons will each be tested by stratified log-rank test. The tests will be stratified by geographic region and MSKCC prognostic groups. The hazard ratio (lenvatinib + everolimus relative to sunitinib and lenvatinib + pembrolizumab relative to sunitinib) and the corresponding 95% CIs will be estimated using the Cox regression model with Efron's method for ties, stratified by the factors used for stratified randomization. The median PFS, and the PFS rates at 6, 12, 18 months, and so on (depending on data adequacy), will be calculated using the K-M product-limit estimates for each treatment arm, and presented with two-sided 95% CIs.

The K-M curve of PFS will be plotted over time.

All primary efficacy analyses will be performed based on Full Analysis Set as the primary analysis set and efficacy analyses performed on the Per Protocol Analysis Set will be considered as the secondary analysis set.

The PFS censoring rules in this SAP (Table 4) and definition of progression date follow the [Food and Drug Administration \(FDA\) “Guidance for Industry Clinical Trial Endpoints for the Approval of Cancer Drugs and Biologics \(2007\)”](#) and [European Medicines Agency \(EMA\) "Guideline on the Evaluation of Anticancer Medicinal Products in Man \(2013\)"](#).

Progression date is assigned to the earliest date when any RECIST 1.1-defined disease progression is observed without missing more than one adequate radiologic assessment.

**Table 4 Censoring Rules for Derivation of Progression-Free Survival**

No.	Situation	Date of Progression or Censoring	Outcome
1	No baseline or postbaseline tumor assessments	Date of randomization	Censored
2	Progression documented between scheduled visits	Date of first radiologic PD assessment	Progressed
3	No progression at the time of data cutoff	Date of last adequate radiologic assessment prior to or on date of data cutoff	Censored
4	New anticancer treatment started	Date of last adequate radiologic assessment prior to or on date of new anticancer treatment	Censored
5	Death before first PD assessment	Date of death	Progressed
6	Death between adequate assessment*	Date of death	Progressed
7	Death or progression after more than one missed visit/tumor assessment**	Date of last adequate radiologic assessment before missed tumor assessments	Censored

CR = complete response, PD = progressive disease, PR = partial response, SD = stable disease.

\* Adequate tumor assessment is radiologic assessment of CR, PR, SD, non-CR/non-PD or PD as determined by investigators at regular interval as defined in the protocol. Any tumor assessments after new anticancer treatment starts will be removed in the definition of PFS.

\*\* More than one missed visit/adequate tumor assessment is defined as having the duration between the last adequate tumor assessment and PD or death being longer than 16 weeks + 10 days (tumor assessment window) - 1 day, which is 121 days for subjects on the every 8 week tumor assessment schedule in this study.

The priority of the censoring rules is as follows:

1. If the subject had PD or death, the following sequence will be applied:

- If a subject did not have a baseline tumor assessment (No. 1), the subject will be censored on the date of randomization. However, if the subject died within 121 days after randomization and did not receive a new anticancer treatment, it will be counted as PFS event at the date of death. If a subject had new anticancer treatment before PD or death (No. 4), the subject will be censored on the date of the last adequate tumor assessment prior to or on the date of new anticancer treatment.
  - If a subject missed two or more tumor assessments before PD or death (No. 7), the subject will be censored on the date of the last adequate tumor assessment before PD or death. Note that if a subject is censored by both this criterion and the anticancer treatment criterion, the earliest censoring date will be used.
  - Otherwise, if a subject had an event (No. 2, No. 5, or No. 6), the earliest event date will be used.
2. If a subject did not have PD or death, the censoring date will be the earliest censoring date if the subject met multiple censoring criteria (No. 1, No. 3, No. 4, No. 7).

Sensitivity analyses will be performed using unstratified log rank tests for comparisons of PFS of lenvatinib + everolimus (Arm A) versus sunitinib alone (Arm C) and lenvatinib + pembrolizumab (Arm B) versus sunitinib alone (Arm C), as well as unstratified Cox proportional hazards model with Efron's method for ties, including treatment arms as a single covariate for the estimation of the hazard ratio. In addition, the following sensitivity analyses will also be performed:

1. Using the actual reported date of progression by IIR or death to define PFS regardless of missing assessments, or use of new anti-cancer therapy (Per EMA guidance);
2. Using the radiologic assessment data as assessed by Investigator and death to define PFS;
3. Using the different derivation rule for the situation with more than one missed visit/tumor assessment: death or progression immediately after more than one missed visit/tumor assessment (i.e. if a subject missed two or more tumor assessments right before PD or death, the subject will be censored on the date of the last adequate tumor assessment before PD or death. Note that if a subject is censored by both this criterion and the anticancer treatment criterion, the earliest censoring date will be used).

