9.5.1.2 Efficacy Assessments

9.5.1.2.1 TUMOR ASSESSMENTS DURING STUDY TREATMENT

Tumor assessments will be performed using RECIST 1.1 (for all subjects). Investigator-determined response assessments will be performed at each assessment time point and entered onto the case report form. Copies of all tumor assessment scans will be sent to an ICL designated by the sponsor for efficacy assessment. Tumor assessments will be carried out following the guidelines provided by the ICL.

Historical CT or MRI scans performed within 28 days before randomization, but before the signing of informed consent, may be used as screening scans, provided they meet minimum standards as separately defined by the ICL.

Tumor assessments (CT chest, and CT or MRI abdomen, pelvis, and other known or suspected sites of disease) will be performed during the Prerandomization Phase and then every 8 weeks from the date of randomization during treatment cycles in the Randomization Phase and as determined by the treating physician in the Extension Phase. The same imaging modality and image-acquisition protocol should be used consistently across all time points. A bone scan (^{99m}Tc-based scintigraphy, whole-body bone MRI, or ¹⁸F-sodium fluoride positron emission tomography [NaF PET]) will be performed within 6 weeks prior to randomization (historical is acceptable), every 24 weeks after randomization, and within a target of 1 week but no more than 2 weeks following a CR as assessed by the investigator. Lesions identified on bone scans should be followed with cross-sectional imaging.

A brain scan (CT of the brain with contrast or MRI of the brain pre- and post-gadolinium) will be performed at screening and as clinically indicated thereafter, and within a target of 1 week but no more than 2 weeks following achievement of a CR. For subjects with a history of protocol-eligible treated brain metastases, a brain scan will be required at all tumor assessment time points (eg, every 8 weeks).

All subjects will be permitted to continue treatment beyond initial RECIST 1.1-defined progression as long as the investigator believes that the subject is still receiving clinical benefit and is tolerating study drug treatment.

Clinical benefit is defined as:

- Absence of signs and symptoms of PD (including labs)
- No decline in performance status
- Absence of rapid progression of disease
- Absence of progressive tumor(s) at critical sites requiring urgent intervention (eg, spinal cord compression)

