### 5.1 Study Endpoints

#### 5.1.1 Primary Endpoint

The primary endpoint is PFS assessed by IIR, defined as the time from the date of randomization to the date of the first documentation of disease progression or death (whichever occurs first) using RECIST 1.1 ([Eisenhauer et al., 2009](#)). PFS censoring rules will follow the FDA guidance of 2007 ([FDA, 2007](#)) and will be detailed in subsequent section.

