## 5.3 Data Analysis General Considerations

Tumor response will be assessed by IIR and the investigator based on RECIST 1.1 for all three arms. Analyses will be performed separately for assessments by IIR and by the investigator, but the primary endpoint is progression-free survival as assessed by IIR.

All stratified efficacy analyses will be based on strata recorded in the IxRS system at randomization as primary. The concordance and discordance of strata between IxRS and the clinical database will be summarized in frequency and percentage by treatment arms and listed by treatment arm and subject.

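### SAP Table 4 lets investigator reads decide which scans count for PFS by independent review, and its missed-scan rule can be read in two ways

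*SAP*

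**What the plan says.** **Assessor.** SAP 5.1.1 states: "The primary endpoint is PFS assessed by IIR". Protocol 9.5.1.2.1 provides the central reader with the scans: "Copies of all tumor assessment scans will be sent to an ICL designated by the sponsor for efficacy assessment". SAP 5.3 keeps the two readers apart: "Analyses will be performed separately for assessments by IIR and by the investigator".

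**Adequacy.** The single-asterisk footnote to SAP Table 4 reads: "Adequate tumor assessment is radiologic assessment of CR, PR, SD, non-CR/non-PD or PD as determined by investigators". No IIR version is given. The term adequate is then used in three places:
- the censoring dates in rows 3, 4 and 7;
- the missed-scan test in the double-asterisk footnote;
- the progression-date rule in SAP 5.4.1, which requires that "disease progression is observed without missing more than one adequate radiologic assessment".

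SAP 5.4.3.1 carries the Table 4 rules over to duration of response (DOR), which SAP 5.1.3 defines by IIR as well as by investigator.

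**Missed scans.** Row 7 covers "Death or progression after more than one missed visit/tumor assessment". The double-asterisk footnote defines this as "having the duration between the last adequate tumor assessment and PD or death being longer than 16 weeks" plus 10 days minus 1 day, given as 121 days. In item 1 of the priority list below the table, the bullet for No. 7 says that "the subject will be censored on the date of the last adequate tumor assessment before PD or death". Item 2 of that list covers subjects with neither progression nor death, yet includes No. 7 among the criteria that may censor them. Sensitivity analysis 3 is labelled a different derivation rule. It adds that the missed scans come immediately before the event, and otherwise uses the same censoring date and the same tie-break note as the item 1 bullet.

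**The concern.** For an endpoint read by IIR, whether a scan was usable should depend on the IIR read. Under the single-asterisk footnote, a visit with no usable IIR result can still bridge a gap or set a censoring date, because the investigator could read the scan. The reverse also happens: a scan that IIR read but the investigator could not is treated as missing. Progression itself is still read by IIR. What can go wrong is event status after a gap, and the censoring date. This touches both PFS hypotheses (H1 and H2) and IIR-based DOR.

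The second issue is that the primary missed-scan rule is not uniquely specified. Two programmers could follow the SAP faithfully and derive different outcomes for a subject who missed scans, resumed them and later progressed. It also leaves unclear whether sensitivity analysis 3 tests anything.

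**Working it through.** **1. The plan's threshold.** 16 × 7 + 10 − 1 = 121 days, which reproduces the SAP figure.

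**2. What one or two lost scans do.** Scans are every 8 weeks (56 days), with a window of ±5 days.
- One unusable scan before progression: 2 × 56 = 112 days, not longer than 121, so no change of status.
- Two in succession: 3 × 56 = 168 days, longer than 121, so the subject is censored.

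These are nominal gaps. With both windows at their limits, one lost scan can reach 112 + 10 = 122 days.

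**3. Worked subjects for the adequacy rule.** In both, the last scan usable to both readers is day 112 and IIR progression is on day 280.

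| Scans on days 168 and 224 | Adequacy by investigator (as written) | Adequacy by IIR |
|---|---|---|
| IIR not evaluable, investigator stable disease | gap 280 − 224 = 56: event, day 280 | gap 280 − 112 = 168: censored, day 112 |
| IIR stable disease, investigator not evaluable | gap 280 − 112 = 168: censored, day 112 | gap 280 − 224 = 56: event, day 280 |

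**4. Size of the first pattern.** The documents give no rate p of scans that IIR cannot evaluate but the investigator can, so a range is assumed. With independent scans and progression found at the first IIR-evaluable scan, a switch needs at least two such scans around progression. A closed-form ceiling is 1 − (1 − p)²(1 + 2p).

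The simulation used document inputs where they exist: 8-weekly scans, exponential medians of 12.3 and 17.2 months, 22% yearly loss, 34-month accrual and cutoff at month 45. It had 400,000 subjects in each of two arms and did not model deaths. The clustered case assumes an intra-subject correlation of 0.2.

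| p | Ceiling | Simulated, independent | Simulated, clustered |
|---|---|---|---|
| 2% | 1 − 0.9604 × 1.04 = 0.118% | 0.098% | 0.774% |
| 5% | 1 − 0.9025 × 1.10 = 0.725% | 0.573% | 2.123% |
| 10% | 1 − 0.81 × 1.20 = 2.800% | 2.239% | 4.833% |

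Monte Carlo standard errors are at most 0.033 percentage points. These are shares of progression events. A death switches only if the last two scans before it are both of this kind, because one leaves at most 56 + 56 = 112 days. With independent scans that is at most p²: 0.04%, 0.25% or 1.0%.

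**5. The two missed-scan rules.** Take scans on days 0, 56, 224, 280 and 336, and progression on day 392.
- *Last gap* (double-asterisk footnote, item 1 bullet, sensitivity analysis 3): 392 − 336 = 56, so an event on day 392.
- *Any gap*: 224 − 56 = 168, longer than 121, so censored on day 56.

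Where the gap falls just before progression (scans on days 0, 56 and 112, progression on day 280), both rules censor on day 112. If scans are missed independently at an assumed 2%, 5% or 10%, with follow-up assumed uniform over 11 to 45 months, the rules classify about 0.13%, 0.80–0.96% or 3.09–3.47% of progressing subjects differently. The ranges cover the two medians.

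**The case against.** **On adequacy.** IIR still calls progression, and SAP 5.3 separates the two sets of analyses, so a programmer might apply IIR adequacy anyway. Sensitivity analysis 1 uses the IIR progression or death date regardless of missed assessments, which limits the consequence for event status. SAP Section 9 places derivation rules in separate documents that were not available here and may already use IIR reads. All of this stands, and it keeps the effect small. It does not make the footnote right: a specification using IIR adequacy would contradict the SAP. Nor can sensitivity analysis 1 isolate the missed-scan rule, because it drops censoring for new anticancer therapy at the same time.

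**On sensitivity analysis 3.** A reader might infer that it simply repeats the primary rule, so that no subject can differ. That holds if the double-asterisk footnote and the item 1 bullet are the whole primary rule, and row 7 does carry that footnote's marker. But the SAP labels the analysis as different, adds wording about the gap being immediately before the event, and lists No. 7 for subjects who have had no event. Those features fit a primary rule triggered by any gap. The row 7 date, before the missed scans, fits either reading. The duplication is therefore conditional; what the documents establish is the inconsistency.

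**Conclusion.** The adequacy footnote is wrong as written for IIR-based endpoints, and confidence in that is high. Its effect is probably small: about 0.1%, 0.6% or 2.2% of progression events at assumed independent rates of 2%, 5% or 10%, and about 0.8%, 2.1% or 4.8% if such scans cluster as assumed. These figures cover one direction of reader disagreement and are not a net effect.

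Two further inferences are not supported. A reader might multiply these rates by the 388 planned PFS events, but those include deaths, for which the rate is lower. A reader might also infer bias towards one arm because the trial is open-label. The documents give no rate of reader disagreement by arm, and no direction of bias or hazard ratio effect is claimed.

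The missed-scan rule is internally inconsistent, with moderate confidence. The text supports a last-gap rule in some places and an any-gap rule in others, and the choice changes outcomes for subjects who resume scanning after a long gap.

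**What to change.** 1. In the single-asterisk footnote, define adequacy by IIR for IIR-based endpoints and by the investigator for investigator-based endpoints. This carries to DOR.
2. State first whether the last gap or any gap is the primary missed-scan rule. Choosing last gap by default could swap the primary and sensitivity rules if any gap was intended.
3. Align the row 7 date, the double-asterisk footnote, the item 1 bullet and the No. 7 entry in item 2 with that choice. Under last gap the item 2 entry goes, because row 7 requires progression or death. Under any gap the footnote and the item 1 censoring date change, and row 7's situation must be widened if No. 7 is to apply to subjects without an event.
4. Make sensitivity analysis 3 the other rule, or delete it.

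The cost is a few wording changes and matching data set specifications before database lock. No new data are needed, and no sample size or event target changes.

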#### 5.4.2 Secondary Efficacy Analyses

All analyses of secondary efficacy endpoints will be performed based on Full Analysis Set as the primary analysis set and Per Protocol analysis set as the secondary analysis set.

1. Overall Survival (OS) will be compared between lenvatinib + everolimus (Arm A) and sunitinib alone (Arm C), and between lenvatinib + pembrolizumab (Arm B) and sunitinib alone (Arm C), using the stratified log-rank test with geographic region and MSKCC prognostic groups as strata. The hazard ratio and its 95% CI comparing lenvatinib + everolimus (Arm A) versus sunitinib alone (Arm C) and lenvatinib + pembrolizumab (Arm B) versus sunitinib alone (Arm C) will be estimated by a stratified Cox proportional hazards model with Efron's method for ties, stratified by geographic region and MSKCC prognostic groups. Median OS

and the OS rate at 12, 18, 24 months, and so on (depending on data adequacy) with 2-sided 95% CIs will be calculated using K-M product-limit estimates for each treatment arm and K-M estimates of OS will be plotted over time. Three interim and a final analyses of OS are planned to be performed (SAP [Section 6](#)). Lan-DeMets spending function with Pocock boundary will be used to control alpha levels among the interim and final analysis of OS (SAP [Section 5.3.3](#)). The first two OS interim analyses will be performed at the time of PFS interim and final analysis, corresponding to approximately 45% and 60% of information fractions of OS events. The third OS interim analysis will be performed at approximately 80% information fraction of OS events. The final analysis of OS will be performed when 304 OS events are observed for each comparison.

All events of death will be included, regardless of whether the event occurred while the subject was still taking study drug, or after the subject discontinued study drug. Subjects who were alive at the data cutoff date will be censored at the data cutoff date. Subjects who were lost to follow-up or withdrew consent will be censored at the date the subject was last known to be alive.

2. Objective Response Rate (ORR), estimated by treatment arms based on the tumor response evaluation by IIR according to RECIST 1.1, will be calculated with exact 95% confidence intervals using the method of Clopper and Pearson. The difference between treatment arms comparing lenvatinib + everolimus (Arm A) versus sunitinib alone (Arm C) and lenvatinib + pembrolizumab (Arm B) versus sunitinib alone (Arm C) will be tested using the Cochran-Mantel-Haenszel (CMH) test, stratified by geographic region and MSKCC prognostic groups. The 2-sided 95% CIs for the odds ratio and the difference in ORR will be calculated. The p-value for hypothesis testing of ORR will be based on the ORR data at the time of the PFS interim analysis. The ORR data available at the subsequent analysis time points will be provided for supportive purposes.

For the adjustment of multiplicity of primary endpoint PFS, key secondary endpoints ORR and OS, please refer to SAP [Section 5.3.3](#). There is no multiplicity adjustment to be made for other secondary and exploratory efficacy endpoints. For statistical tests to be performed on other secondary and exploratory efficacy endpoints, nominal p-values will be generated.

PFS2 will be evaluated using K-M estimates and difference in PFS2 will be tested by stratified log-rank test, stratified by geographic region and MSKCC prognostic groups. The hazard ratio (lenvatinib + everolimus relative to sunitinib and lenvatinib + pembrolizumab relative to sunitinib) and the corresponding 95% confidence intervals (CIs) will be estimated using the Cox regression model with Efron's method for ties, stratified by the same stratification factors. Patients alive and for whom a disease progression on second line therapy has not been observed will be censored at the last time known to be alive. Subjects who did not have second line therapy and no death documented before data cutoff date will be censored at the data cutoff date. Time to next-line therapy will be summarized only for subjects who experience the next-line therapy. It is defined as the time between

randomization and the start date of next-line therapy. The median and quantile of time to initiation of next-line therapy will be summarized.

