9.1.2.2 Follow-Up Period

The Follow-up Period will begin the day after the Off-Treatment Visit and will continue as long as the subject is alive, unless the subject withdraws consent, is lost to follow-up, or the sponsor terminates the study. If a subject discontinues study treatment and does not consent to continued follow-up, the investigator must not access confidential records that require the subject's consent. However, an investigator may consult public records to establish survival status.

During the follow-up period, subjects will be treated by the investigator according to the prevailing local standard of care. Subjects will be followed every 12 weeks (\pm 1 week) for PFS2, survival, and all subsequent anticancer treatments received. This information will be recorded unless this information is not allowed to be provided due to confidentiality. The

sponsor may choose to discontinue survival follow-up following completion of the primary study analysis when appropriate, eg, when only a minimal number of subjects remain in follow up.

If a subject becomes unavailable for follow-up (eg, misses scheduled assessment, telephone contact), the investigator or designee will make every attempt to contact the subject to determine his or her status. All attempts at contact will be recorded in the subject's medical notes. Subjects will only be deemed lost to follow-up:

- After a minimum of 3 attempted contacts (eg, telephone, letter) with the subject, the subject's family, or the primary care (family) physician, at least 4 weeks apart. The last attempt at contact must occur no earlier than 3 months after the subject's last successful contact.
- If the last attempt at contact is unsuccessful, the site should write a letter with certified proof of posting to the subject, subject's family, or the primary care (family) physician to request information on the subject's status, if regionally required.

All subjects who discontinue study treatment prior to disease progression will continue to undergo tumor assessments every 8 weeks and a bone scan every 24 weeks in the Follow-up Period, until disease progression is documented and confirmed by IIR or a new anticancer therapy is initiated, unless the subject withdraws consent or is lost to follow-up.

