Summary statistics of the scores for the derived functional / symptom scales according to the scoring manual and global health status scores will be summarized by treatment arm at each time point. A separate pre-specified HRQoL analysis following FDA and EMA PRO Guidelines will be performed and detailed in a separate SAP and HRQoL report. Scoring of EQ-5D-3L and derivation of utility for health economic analysis will also be accomplished in a separate analysis and described in a separate HRQoL report.

PFS2 will be calculated using the Kaplan-Meier (KM) product-limit estimates for each treatment group and presented with two-sided 95% CIs. The KM estimate of PFS2 will also be plotted over time for each treatment group.

PFS by investigator assessment per RECIST v1.1 will be analyzed similarly as for the primary endpoint of PFS by IIR per RECIST v1.1.

The strategy to address multiplicity and control of the overall FWER for the primary and key secondary efficacy endpoints is described in [9.7.4](#).

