#### 5.1.2 Secondary Endpoints

- Objective response rate (ORR), defined as the proportion of subjects who have best overall response (BOR) of CR or PR as determined by IIR using RECIST 1.1. ORR will be calculated for confirmed CR/PR, and for confirmed and unconfirmed CR/PR. Confirmed CR/PR will be primary for ORR analysis.
- Overall survival (OS), defined as the time from the date of randomization to the date of death from any cause. Subjects who are lost to follow-up and those who are alive at the date of data cutoff will be censored at the last date the subject was last known alive, or date of data cutoff, whichever occurs first.
- Safety will be assessed summarizing the incidence of treatment-emergent adverse events (TEAEs) and SAEs together with all other safety parameters.
- Proportion of subjects who discontinue treatment due to toxicity is defined as the proportion of subjects who discontinue study treatment due to treatment-emergent adverse events (TEAEs).
- Time to treatment failure is defined as time from the date of randomization to the date that a subject discontinues study treatment due to TEAEs.
- Health-Related Quality of Life (HRQoL), assessed using the Functional Assessment of Cancer Therapy Kidney Syndrome Index-Disease-Related Symptoms (FKSI-DRS), the European Organization for the Research and Treatment of Cancer (EORTC) QLQ-C30 and the European Quality of Life (EuroQOL) EQ-5D-3L instruments. This analysis will be detailed in a separate SAP for HRQoL.
- PFS on next-line therapy (PFS2), defined as the time from randomization to disease progression on next-line treatment or death from any cause (whichever occurs first).
- Progression-free survival (PFS) by investigator assessment is defined as the time from the date of randomization to the date of first documentation of disease

progression based on the investigator assessment per RECIST v.1.1 or death (whichever occurs first).

- Pembrolizumab PK comparison to historical data. This analysis will be detailed in a separate SAP for PK/PD.
- Model-predicted clearance and AUC for lenvatinib in Arms A and B. This analysis will be detailed in a separate SAP for PK/PD.
- Model-predicted clearance and AUC for everolimus in Arm A. This analysis will be detailed in a separate SAP for PK/PD.

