### 5.2.2 Subject Disposition

Enrolled subjects include all subjects who signed informed consent forms. The number of subjects screened and the number (percent) of subjects who failed screening and the reasons for screen failure will be summarized, based on data reported on the Screening Disposition Case Report Form (CRF).

The number of subjects randomized, treated, prematurely discontinued from study drug, and those with major protocol deviations will be counted by site and by treatment arms. The number of subjects who discontinued one medication but remained on other medication in Arm A and Arm B will also be summarized. The primary reason for study drug discontinuation will be summarized by treatment arms and overall according to the categories in the corresponding CRFs.

The end of study status: alive (still on treatment or on follow up), death, withdrew consent, lost to follow-up or study terminated by sponsor at the data cutoff date will also be summarized by treatment arms and overall.

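### The PFS2 censoring rule in SAP 5.4.2 carries lost and withdrawn subjects event-free to the data cutoff

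*SAP*

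**What the plan says.** SAP 5.1.2 defines PFS2 as time from randomization to progression on the next line of treatment or death from any cause. SAP 5.4.2 then gives two censoring sentences. The first covers living patients "for whom a disease progression on second line therapy has not been observed will be censored at the last time known to be alive". The second reads "Subjects who did not have second line therapy and no death documented before data cutoff date will be censored at the data cutoff date". Neither mentions loss to follow-up or withdrawal of consent.

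The same section does deal with these subjects for OS: "Subjects who were lost to follow-up or withdrew consent will be censored at the date the subject was last known to be alive". SAP 5.1.2 says of OS that those lost or alive "will be censored at the last date the subject was last known alive, or date of data cutoff, whichever occurs first". For PFS, the priority rules under SAP Table 4 state that, for a subject without an event, "the censoring date will be the earliest censoring date if the subject met multiple censoring criteria". Protocol 9.7.1.6.2 says only that "PFS2 will be calculated using the Kaplan-Meier (KM) product-limit estimates for each treatment group" and gives no PFS2 censoring rule. SAP 5.2.2 already tabulates subjects who "withdrew consent, lost to follow-up or study terminated by sponsor at the data cutoff date".

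**The concern.** A subject can be counted as free of PFS2 events only while vital status and next-line treatment are being observed. Someone lost at month 6, with no second-line therapy on record and no death on file, is sent by the second sentence to the data cutoff, possibly years later. Missing information is then treated as absence of the event. Once a subject has refused further follow-up, the investigator may consult public records, but only for survival status (Protocol 9.1.2.2, SAP 3.2). A second-line start or progression on it would go unseen.

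The PFS2 curves, medians and quartiles would be too high. The hazard ratio would shift if one arm lost more subjects than the other, which cannot be excluded in an open-label trial.

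**Working it through.** **Reading the rules.** Take a subject lost before second-line therapy, with no documented death.

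- If the first PFS2 sentence is general, it gives the date last known alive and the second gives the cutoff. The SAP states no precedence.
- If the first sentence covers only subjects who started second-line therapy, the second sentence alone applies and the date is the cutoff.
- The loss and withdrawal rule is written for OS. The earliest-date rule refers to the numbered PFS situations in Table 4. The Protocol is silent. None of them supplies an exception for PFS2.

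**Inputs.** The plan gives no PFS2 sample size, event count or power, so there is no PFS2 figure to reproduce. The borrowed inputs come from SAP Section 4: 34-month accrual, PFS cutoffs at about months 38 and 45, PFS medians of 12.3 and 17.2 months (HR 0.714), and 3% yearly loss to follow-up (the OS assumption). The PFS inputs agree with the plan's own figure: Freedman's formula at two-sided alpha 0.045 and 90% power gives (2.005 + 1.282)² × (1.714/0.286)² ≈ 388 events, as stated.

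**Share affected and time credited (closed form).** Let λ = −ln(0.97)/12 = 0.002538 per month be the loss rate, and let μ = ln 2/median be the rate of reaching second-line therapy, with its median *assumed* equal to the planned PFS median. Put k = λ + μ. For a cutoff at month 45, potential follow-up F is uniform on 11 to 45 months, with mean 28.

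Share lost first = (λ/k) × (1 − E), where E = (e^(−11k) − e^(−45k))/(34k).

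Mean time credited per affected subject = [28λ/k − (λ/k²)(1 − E)] / share.

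| Arm | μ | k | λ/k | E | Share | Of 350 | Months credited each |
|---|---|---|---|---|---|---|---|
| Sunitinib (12.3) | 0.05635 | 0.05889 | 0.0431 | 0.2260 | 3.3% | 12 | 19.2 |
| Test (17.2) | 0.04030 | 0.04284 | 0.0593 | 0.3287 | 4.0% | 14 | 18.4 |

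**Effect on PFS2 (simulation, 400,000 subjects per arm and scenario).** The written rule was compared with censoring at the time of loss. Assumptions not in the documents: 60% or 80% start second line; second-line median 8 or 15 months; subjects without second line either die at the end of first line or live on with median 9 months; median 10 months from second-line progression to death. The main case uses 12.3/17.2 months to second line. The full grid also uses 9 and 15 months in the control arm, with HR 0.714.

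| Month 45 | Main case | Full grid |
|---|---|---|
| Share of an arm | 3.3–4.6% (12–16 of 350) | 2.7–4.9% (9–17 of 350) |
| Months credited each | 18–19 | 17.6–20.3 |
| Median shift, no later deaths found | +0.5 to +1.6 | +0.3 to +2.2 |
| Median shift, half found | +0.3 to +1.1 | +0.2 to +1.5 |
| Median shift, all found | +0.2 to +0.7 | +0.1 to +0.9 |

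Over the grid the arm hazard is 2.9–3.8%, 1.8–2.6% or 0.3–1.5% too low with none, half or all of the deaths found. At month 38, 2.4–3.9% of an arm gains 14.0–15.6 months each, and the median rises by 0.3–1.6 months with no deaths found. The HR stays within 0.4% throughout, because loss is equal by arm.

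**Unequal loss (sensitivity only).** With every subject starting second line, a 12-month median from then to the PFS2 event and a cutoff at month 45, yearly loss of 10% in the test arm and 3% under sunitinib moves the HR from 0.759 to 0.682. Reversing the rates moves it from 0.761 to 0.842. The documents give no arm-specific rates.

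**The case against.** The first PFS2 sentence, read literally, fits a subject lost before second-line therapy and gives the right date, so the fault might be only an unresolved overlap. The SAP also leaves derivation detail to data set specifications (SAP 8.1.1 and Section 9), which could settle it. The overlap is real, but the second sentence is the more specific of the two, and a specification outside the SAP should not have to overrule a rule stated in it.

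Some later deaths will be found. A subject is deemed lost only "After a minimum of 3 attempted contacts (eg, telephone, letter) with the subject", the subject's family or the family physician, and the sponsor may request survival updates (Protocol 9.1.2.2 and 9.1.3.2). That lowers the bias without removing it, as the half-found and all-found rows show.

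The practical effect is modest. In the main case the 95% sampling half-width of a PFS2 median with 350 subjects is about 2.5–5.2 months, and the shift with no deaths found is roughly one fifth to one third of that. PFS2 is outside the multiplicity scheme. This stands and limits the weight of the point. Still, the bias is systematic and would not shrink with more subjects.

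The strongest remaining objection is to the remedy: a subject traced alive may have started second line and progressed unseen, so moving the censoring date forward again credits unobserved time. That is true. If half of lost subjects are traced, the remedy leaves the hazard 0.1–0.8% too low (median +0.05 to +0.5 months). If all are traced, it coincides with the present rule. It was never worse than the present rule, and it follows the SAP's own OS convention.

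**Conclusion.** The concern holds. As written, SAP 5.4.2 sends subjects lost or withdrawn before second-line therapy to the data cutoff, and the overlapping sentence adds a conflict without curing this. Kaplan-Meier PFS2 is biased upward, by about 0.5–1.6 months in the median in the main case if no later deaths are found and less if they are. The direction follows from the text. The size rests on the 3% yearly loss borrowed from OS planning and on assumed second-line parameters. The PFS2 hazard ratio is essentially unchanged under equal loss and could move either way under unequal loss. The PFS, OS and ORR tests and the sample size do not depend on this rule. The change should be made, but it does not threaten the trial's main conclusions.

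**What to change.** Replace both PFS2 censoring sentences in SAP 5.4.2 with one: *Subjects without a PFS2 event, whether or not they started second-line therapy, including those lost to follow-up or who withdrew consent, will be censored at the date last known to be alive or the data cutoff date, whichever occurs first.* Define the date last known alive for subjects still on study treatment as well.

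State that later survival checks are used symmetrically: a death found is an event on its date, and a survivor found moves the censoring date. Counting deaths while ignoring survivors would overstate the hazard by 0.3–1.1% (half traced) or 0.6–2.3% (all traced).

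The cost is a change of SAP wording and one derivation. Lost and withdrawn status at the cutoff is already summarized under SAP 5.2.2, and the date last known alive is already needed for OS.
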